4.10.2 Qualitative analysis

Self-reported patient experience will be examined at 6 months using qualitative methods. Interview transcripts will be imported into NVivo for thematic analysis. Initial open coding of transcripts will be undertaken iteratively by members of the research team. Themes and care quality measures will be presented to the broader research team and program implementers for final consensus.

4.10.3 Economic analysis

The analysis will be conducted from a health service perspective (base case) and a societal perspective including direct and indirect costs from the health-consumer's perspective - out of pocket expenses for any medicines or products provided, waiting time and travel time to attend treatment, productivity gains or time lost from work.

The scope of the within-study cost analysis is constrained by the design of the cohort study. Cost items associated with the co-design process, research and evaluation will be excluded. Resource use associated with the 2 components, pharmacy enrolment, training and support and pharmacy consultation, will be prospectively identified, measured and valued. In measuring resource use associated with delivery of the intervention, data will be collected from the research team, from the enrolled pharmacies and from the enrolled patients. Labour time will be measured using opportunity costs and valued based on Pharmacy Industry Award rates of pay, and average earnings for patients.

Results from the economic analysis will be expressed as (1) net benefit in terms of implementation costs and cost savings arising from more efficient treatment pathways; and (2) cost-consequence results accounting for patient experience measures, relevant safety outcomes and implementation measures.

[figure not shown]
Decision uncertainty will be accounted for using parametric and non-parametric bootstrapping to generate uncertainty intervals around the net benefit result.

4.10.4 Implementation outcomes analysis

The implementation component of the study will be underpinned by the Consolidated Framework for Implementation Research (CFIR) [9-12], the use of an adapted implementation model for community pharmacy [13-23]. Implementation factors (barriers, causes and facilitators) (Appendix 3) and the Dougherty strategy classification systems (Appendix 4), adapted to community pharmacy, will be used [13-23]. This will build on the trial outcomes to determine scalability of the intervention. The evaluation framework is set out in Figure 1. The CFIR domains and sub-domains will also be used to organise the data. Descriptive statistics be produced for all implementation outcomes. Links between implementation barriers and facilitators, their

cause and implementation strategies will be visually represented using Sankey diagrams. A predictive resolution percentage will be calculated using random forest method for predicting effective strategies for all implementation barriers.

Figure 1 Implementation Evaluation Framework adapted from Moullin, et al. [13]

4.11 Oversight and management of serious adverse events

The establishment of a Data Safety Monitoring Board (DSMB) is an essential step in ensuring the safety and integrity of a research study or clinical trial. The DSMB is an independent committee responsible for the ongoing monitoring of the study and making informed decisions regarding participant safety. One of the primary functions of the DSMB will be to review and evaluate any serious adverse events that occur during the study. Serious adverse events refer to unexpected or severe adverse reactions, complications, or other medically significant incidents experienced by participants. Furthermore, the DSMB will be responsible for assessing the overall safety profile of the study. The internal adverse events policy and procedure for the UTI and OC trials will be extended (Appendix 25) for this trial. It will analyse the frequency and severity of adverse events, identify any emerging patterns or trends, and evaluate whether the study intervention poses any risks that outweigh its potential benefits. The DSMB will also review the safety data in relation to the study's objectives and may make recommendations to modify or discontinue the study if warranted. The DSMB will report its findings and recommendations to the UoN HREC. The DSMB's report to the HREC will include information on serious adverse events, their assessment, and any recommendations regarding participant safety or modifications to the study protocol. During the period before the establishment of the DSMB, the responsibility for reviewing and reporting serious adverse events falls to the Project Steering Committee. The committee already established for the PATH-UTI and PATH-OCP will be extended to cover PATH-DERM trial.

5. Ethical Considerations

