4.4.2 Participant (patient) inclusion criteria

The age requirements for participation vary depending on the condition:

- Mild to moderate atopic dermatitis, 6 months to 65 years old
- Herpes Zoster (Shingles), 18 years and older
- Impetigo, 12 month or above
- Mild plaque psoriasis, 18 years and older

If an individual meets the age requirements for their condition, the pharmacist may offer them participation in the trial and provide a consultation. This consultation could lead to (i) referral to a medical professional and/or (ii) an appropriate management and treatment plan, which may involve pharmacotherapy, supportive therapy, and general advice.

Specific referral criteria for each of the four skin conditions are outlined in the co-designed clinical guidelines for NSW/ACT in Appendix 2. These guidelines clearly define when and to whom timely referral should be made.

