4.9 Outcomes

Primary outcome

The primary outcome will be symptom resolution/relief (completely resolved, improvement, no improvement or worsening) (based on self-report at various time frames at follow up depending on the condition). This will be a composite measure based on patient self-reported data. As symptom resolution/relief time can be different for each of the four conditions, follow-up periods according to the clinical practice guidelines will be:

- 7 days for Impetigo, Psoriasis and Herpes Zoster (Shingles)
- 14 days for Atopic Dermatitis

Secondary outcomes

Secondary outcomes will be:

- Types of medication supplied for each condition by pharmacists. This is a participant specific outcome.
- Adherence rates to treatment protocol. This is a pharmacy-specific outcome.
- Numbers of patients supplied medications by pharmacists. This is a participant specific outcome.
- Numbers of patients provided self-care advice. This is a participant specific outcome.
- Numbers of patients referred to another health professional. This is a participant specific outcome.
- Reasons for patient referral to another health professional. This is a participant specific outcome.
- Estimated duration of consultation. This is a pharmacy specific outcome.
- Patient follow-up rate. This is a participant specific outcome.
- Patient adverse events. This is a participant specific outcome.
- Patient experience. This is a participant specific outcome.
- **Safety outcomes:** Patient-reported adverse events defined as any unfavourable and unintended sign, symptom or disease associated with the use of a medicine, which does not necessarily have to be caused by that medicine (Appendix 25).
- **Implementation outcomes**
 - Patient and provider program participation rates
 - Patient demographics (gender, DOB, education, employment status)
 - Numbers of patients per pharmacy assessed as eligible for pharmacy medication supply.
 - Numbers of patients supplied medication by pharmacists.
 - Estimated duration of consultation
 - Estimated time to complete all service requirements.
 - Adherence rates to treatment protocol
 - Prescriptions for first-line medications for the four skin conditions /Total medication prescriptions for the four skin conditions
 - Classification of appropriateness of medications for the four conditions as aligned with clinical practice guidelines.

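### The serious adverse event definition in 4.11 uses expectedness and severity in place of seriousness, and it does not fit the medicine-bound adverse event definition in 4.9, which leaves part of the service's possible harm outside the safety outcome

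*Protocol*

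**What the plan says.** Two places in the protocol body define the events that make up the safety assessment, and both cite Appendix 25.

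- **Section 4.9, safety outcomes:** "Patient-reported adverse events defined as any unfavourable and unintended sign, symptom or disease associated with the use of a medicine", with the qualifier "which does not necessarily have to be caused by that medicine".
- **Section 4.11, serious events:** "Serious adverse events refer to unexpected or severe adverse reactions, complications, or other medically significant incidents experienced by participants".

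Section 4.11 also says what these events are used for: "One of the primary functions of the DSMB will be to review and evaluate any serious adverse events that occur during the study". The board's remit extends to non-serious events as well: "It will analyse the frequency and severity of adverse events, identify any emerging patterns or trends". Its report to the HREC covers serious events and their assessment. Until the board is in place, the Project Steering Committee reviews and reports serious events.

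On what the patient may receive, section 4.4.2 says: "This consultation could lead to (i) referral to a medical professional and/or (ii) an appropriate management and treatment plan". The consultation form in section 4.6.1 offers tick boxes for non-drug management, for counselling and for no intervention. It also asks whether the patient chose not to buy what was recommended.

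**The concern.** There are two linked problems.

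First, the 4.11 sentence merges attributes that safety reporting keeps apart. Severity is how intense an event is, expectedness is whether it was foreseen, and a reaction implies a causal link. None of these says whether the event had a serious consequence. The body text names no consequence, such as death or hospital admission, that would make an event serious.

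Second, the two definitions differ in scope. Section 4.9 requires a link to a medicine and a report from the patient. Section 4.11 requires neither.

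What is being tested is pharmacist assessment, treatment and referral, and a drug is only one possible part of that. Objective 3 concerns the safety of the intervention, the hypothesis in 4.1 is that the services carry no safety risks, and the board must judge the risks of the intervention as a whole. For a service of this kind, a missed diagnosis or a late referral is a main route to harm, and it needs no medicine. A safety outcome defined through medicine use cannot count that harm when no medicine was used.

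**Working it through.** The protocol states no adverse event rate, serious event rate or safety threshold, so there is no figure to reproduce. The check sets the two definitions side by side and applies them to hypothetical events.

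**Terms of each definition**

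| Feature | 4.9 adverse event | 4.11 serious adverse event |
|---|---|---|
| Source | patient report | not limited |
| Link to a medicine | required | not required |
| Causation | expressly not required | implied by reactions; not by complications or incidents |
| Severity | not used | one route to serious |
| Expectedness | not used | one route to serious |
| Outcome criteria | none | none |

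**Applied to hypothetical events**

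| Event | 4.9 | 4.11 |
|---|---|---|
| Mild, unexpected reaction to a supplied medicine | adverse event | serious if read literally; not serious if the closing words on medical significance govern the whole list |
| Short-lived but intense reaction with no lasting consequence | adverse event | the same two readings |
| Hospital admission, during medicine use, from an unrelated cause | adverse event on the usual reading, if the patient reports it | not a reaction; serious only if accepted as a complication or incident |
| Missed diagnosis with significant harm, no medicine used | not an adverse event | could be serious, as an incident |
| Lesser harm after advice alone, no medicine used | not an adverse event | not serious |

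**What follows**

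1. The first two rows have two defensible answers under 4.11. The sentence joins unexpected and severe with *or*, so either is enough on a literal reading. Two assessors, or the Steering Committee and later the DSMB, could classify the same event differently.
2. The third row depends on which word in the 4.11 list is applied, because reactions imply cause while the later terms do not.
3. The fourth row can be serious without being an adverse event. Serious events are therefore not a subset of adverse events, and a table of serious events could hold cases missing from the table of all events.
4. The fifth row is in neither definition. Such an event might surface as a worsening in the primary outcome or as additional care in the follow-up survey (4.6.2), but not as a safety outcome.
5. Rows four and five are not remote. Sections 4.4.2 and 4.6.1 provide for consultations that end without a medicine, and for patients who decline to buy one.

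**The case against.** **Appendix 25 may settle the matter.** Both sections cite it, and 4.11 says the policy of the two preceding trials is extended to this one. Outcome-based criteria and coded fields may well be there. Its text is not shown, so it cannot be said to lack them. This stands as a limit on the point. It does not remove the mismatch, because two body sections that cite the same appendix still disagree with each other, and section 5.2 requires the approved protocol to be followed as written.

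**The 4.11 sentence can be read more narrowly.** Its closing reference to *other* incidents of medical significance suggests that the earlier items must be medically significant too. On that reading a trivial unexpected reaction is not serious. The reading is reasonable, so it cannot be claimed that every mild surprise must be counted as serious. What stands is that the wording allows both readings.

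**Non-medicine harm is not lost.** A medically significant incident in a patient given no medicine fits 4.11 and can reach the DSMB. That is correct. The gap is in the 4.9 safety outcome and in lesser harm of the same kind.

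**The DSMB does not rely on the serious label.** It also looks at the frequency, severity and pattern of all adverse events, and it reviews serious events case by case. Over-inclusion would add cases to assess. This lowers the stakes, but if the 4.9 definition governs that wider review, patients without a medicine remain outside it.

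**Patient adverse events also appear in 4.9 as a separate secondary outcome with no stated medicine limit.** True, but the only definition of an adverse event in the body is the medicine-bound one.

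**Conclusion.** The point holds as a defect of definition and scope. The 4.11 sentence uses expectedness and severity in place of seriousness and gives no outcome criterion. It does not fit 4.9, whose safety outcome omits harm in patients who used no medicine. Classification sent to the DSMB and HREC may therefore be inconsistent, and the defined safety outcome falls short of objective 3.

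A reader might infer that the serious event counts will be wrong, or that genuine serious events will be diluted many times over by mild ones. The documents do not support either inference. They give no event rates, no expected number of survey responders and no threshold that uses a serious event count. The 22,857 consults are a cap with an alternative closing date, not an expected sample. A dilution factor would only restate assumed rates, and would also need the literal reading of 4.11.

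The conclusion rests on the body text being applied as written, and on some consultations ending without medicine use, which the protocol provides for but does not quantify. If Appendix 25 already holds outcome-based definitions that cover the whole service, the remaining task is to bring 4.9 and 4.11 into line with it. The change should be made because safety is a stated objective, but the point does not undermine the design.

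**What to change.** Use one set of definitions in 4.9 and 4.11, and reconcile both with Appendix 25:

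- **Adverse event:** any untoward medical occurrence after the consultation, whether or not a medicine was supplied, used or thought to be the cause.
- **Serious:** defined by outcome, meaning death, threat to life, hospital admission or its prolongation, lasting disability, congenital anomaly, or another medically important event. Every serious event is then also an adverse event.
- **Separate fields:** severity, expectedness and relatedness, with relatedness assessed against the service (assessment, advice, referral) as well as against any medicine.

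State that the same definitions apply whether the Steering Committee or the DSMB is reviewing. If events have already been recorded, reclassify them under the agreed definitions.

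The cost is two reworded definitions, a check against Appendix 25, and a few coded fields if the event form lacks them. If the HREC regards the change as significant, it goes through the amendment route in section 5.3. The broader definition will bring in more unrelated events, which the relatedness field is there to sort.

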5.1 Research ethics approval

This research protocol will be submitted to the University of Newcastle HREC for ethical review and approval.

5.2 Protocol adherence

Except for changes to eliminate an immediate hazard to participants, the approved protocol will be followed as specified. Any significant protocol deviation or violations will be documented, and notification sent to the UoN HREC as soon as possible.

5.3 Protocol amendments

Any significant change in the study protocol will require an amendment. The Chief investigator will submit this to the University of Newcastle HREC for review and approval. The approval letter, signed by the HREC Chair, will refer specifically to the investigator, the protocol number, the protocol title, the protocol amendment number, and the date of the protocol amendment. The protocol amendment may be implemented only after it has been approved by the HREC. If the revision is an administrative change (such as the addition or removal of committee members), a letter explaining the change(s) along with a copy of the amended pages(s) of the protocol will be submitted to the HREC for their information.

5.4 Notification of study closure

In addition to interim reports as required by the HREC, the Coordinating Principal Investigator will complete a final report notifying the HREC of the conclusion of the study. This report will be made within 3 months of completion or termination of the study.

5.5 Records retention

The Site investigator (or The George Institute for Global Health, on behalf of the Investigator) shall retain and preserve one copy of all data generated during the study for 15 years following study closure.

5.6 Confidentiality

All data collected for the purposes of the study will be kept confidential and will only be accessible by Study Personnel. Data will be maintained in accordance with the National Privacy Act 1998 and the NSW Health Records and Information Privacy Act 2002.

5.7 Dissemination policy

Results will be published in the academic literature and presented at national and international conferences, media articles and newsletters. Publication of the main report from the study will be in the name of the research group, with each individual study investigator named personally at the end of the report.

All participants will be able to request a resume of study outcomes through the trial mailbox, as stated in the PIS and consent forms.

6. Appendices

A list of appendices will be added as attachments to this application:

Appendix 1	NSW Health Authority
Appendix 2	Clinical guidelines
Appendix 3	Implementation Barriers, Facilitators and Causes (CFIR)

Appendix 4	Dougherty strategy classification systems
Appendix 5	Email Communications
Appendix 6	Participant Information Statement (Pharmacy – NSW)
Appendix 7	Consent Form (Pharmacy – NSW)
Appendix 8	Participant Information Statement (Pharmacy – ACT)
Appendix 9	Consent Form (Pharmacy – ACT)
Appendix 10	Participant Information Statement (Pharmacist – NSW)
Appendix 11	Consent Form (Pharmacist – NSW)
Appendix 12	Participant Information Statement (Pharmacist – ACT)
Appendix 13	Consent Form (Pharmacist – ACT)
Appendix 14	Licence form ACT
Appendix 15	Ministry of Health Draft Flyer
Appendix 19	Consent Form (Patient – ACT)
Appendix 20	Patient follow up data collection
Appendix 21	Implementation checklist
Appendix 22	Interview questions (Community participants)
Appendix 23	Interview questions (Community pharmacists and other stakeholders)
Appendix 24	Indicative script for contacting patient participants
Appendix 25	Adverse Events - Policy and Process

7. References

1. NSW Health. (2022). Pharmacy reform to expand community health care. Accessed via: https://www.health.nsw.gov.au/news/Pages/20221113_00.aspx.
2. Ministry of Health (2016). Pharmacy Action Plan 2016 to 2020. Available at: <https://www.health.govt.nz/publication/pharmacy-action-plan-2016-2020> (accessed 21 November 2018).
4. Pharmacy Guild of Australia. (2017). Pharmacists in 2025. Accessed via: https://www.guild.org.au/_data/assets/pdf_file/0022/45454/PGA_CP2025_intro-paper.pdf.
